pedometer step counts (i.e., the “reward”) as well as other “state” information (Figure 1) also collected via IVR. Importantly, the RL algorithm will learn not only based on each patient’s own treatment response, but will incorporate experience from the response of other patients who have similar characteristics and response trajectories as indicated by the “state space.” See Appendix A for a more detailed discussion of RL and the use of state data. Based on this feedback loop, the RL engine will modify the probability distribution across treatment choices and make recommendations for each patient each week. Because actions will be probabilistic rather than “hard-wired,” the AI-CBT program will avoid potentially over-reactive treatment changes that can result when therapists attempt to tailor care non-systematically or using deterministic flow diagrams. All patients will begin with a standard one-hour CBT session. Based on their progress as measured by feedback on the “reward” and “state” features, patients who progress toward functional goals will be moved through less resource intensive options, and patients who need more intensive follow-up will be moved automatically to more time-intensive, therapist-delivered CBT.

B.8 Prior Work by the Investigators

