This will be a randomized non-inferiority study comparing standard pain CBT to a strategy that uses mobile health technology and artificial intelligence in conjunction with trained CBT therapists to deliver evidence-based, stepped pain therapy. Patients in both groups will receive CBT delivered via telephone by trained pain CBT therapists. For patients in the standard CBT group, the therapist will deliver 10 hour-long CBT sessions based on content used throughout VA. Patients randomized to the AI-CBT treatment group will begin with an IVR session and will be asked to report their pedometer-measured step-counts, pain-related functioning, and CBT skill practice via five-minute daily IVR calls. Some of those IVR calls also will include reminders regarding the dates and modalities for upcoming CBT sessions. Based on patients' IVR feedback, AI-CBT will make recommendations to carefully step-up the intensity of each patient's CBT follow-up using more brief telephone therapy sessions (15 minutes), or hour-long therapy sessions with the CBT therapist, if necessary. Based on experience gained from each patient's own history and the overall population of patients, the AI-CBT engine will seek to optimize the population's total improvement in functioning while maintaining each patient at the least resource-intensive mode of CBT delivery. Outcomes will be measured via telephone survey at three and six months post recruitment, and additional data will be collected via clinical records. We will use data from therapists' activity logs and administrative files to conduct a budget impact analysis. Additional data to aid translation of study findings into practice will be collected via qualitative interviews with CBT therapists, PACT team members, and patients with various levels of program response.

D.2 Patient Identification and Recruitment

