Daily IVR Reports. We will collect reports about patients' pedometer-measured step counts, CBT skill practice, and pain-related functioning via daily five-minute IVR calls. If the initial call is missed, the system will automatically try again 15 minutes later and again 1 hour later. We have successfully used these methods in studies achieving high patient response rates. Step counts will measure activity over the prior 24 hours, and patients will report their skill practice using a 0 -10 scale. Pain-related functioning will be assessed using a single item from the West Haven-Yale Multidimensional Pain Inventory (WHYMPI).⁶⁶ Practice of target behaviors will be measured using a 0 (not at all accomplished) to 10 (completely accomplished) scale and items that we have successfully used in our ongoing trial of IVR CBT. Step counts will be used in the "reward function" that the RL algorithm will seek to optimize; and functioning and skill practice reports will be used as "state" information (see Appendix A) that the system will take into account when making decisions that optimize patients' treatment course. The AI system will be able to accommodate missing IVR reports, and patients who fail to complete more than 50% of the daily IVR calls in a two week period will be called by a research associate to trouble shoot problems and encourage compliance with feedback. In addition to being the source of data with which AI-CBT will personalize each patient's course of treatment, web-based reports of data from IVR calls will be used to inform therapists of participants' progress. These data will be particularly important for informing the abbreviated 15 minute therapist sessions where a priority will be placed on the efficient use of treatment time, and during the IVR sessions where the entire session will be pre-recorded. Once a week the IVR call will include a brief message alerting patients of the date, time, and modality for their subsequent week's session.

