Role of the Expert Panel. The AI-CBT program will be supervised with ongoing input from an Expert Panel comprised of experts in: pain management, CBT for chronic pain, clinical trials using behavioral interventions, adaptation of psychotherapy for telephone delivery, and IVR (see Appendix E and letters of

support). The Panel will be directed by [name] (Co-I) who has led many large and geographically-dispersed panels of experts in pain research and treatment, and will ensure that the panel meetings are efficient and effective. The Panel will meet regularly by teleconference during the start-up period to review and revise the treatment materials and refine the AI algorithm to reflect any constraints that should be put into place to limit the choices the algorithm can make, e.g., "if the patient's activity level decreases more than 20% two weeks in a row, recommend two hour-long CBT session regardless of what the prior week's contact was." After start-up, the Panel will teleconference quarterly and in ad hoc sessions as needed.

D.7 Measurement

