Preplanned Subgroup Analysis. Because AI-CBT will continue to learn patterns in patients' experience throughout the intervention period, we hypothesize that the second 50% of patients randomized will show an even larger difference in clinician time than the first 50%, while still demonstrating non-inferiority in pain-related outcomes. Differences in pain related functioning and in clinician treatment time across treatment groups will be tested in this subgroup analysis after stratifying the sample into early versus later recruits.

Approach to Missing Data. If more than 15% of a covariate is missing, we will use multiple imputation methods based on the SAS MI Procedure. We will check if the pattern of missingness is monotonic (i.e., if patients missing data at 3 months also have missing data at 6 months) and use a Markov chain Monte Carlo method that assumes multivariate normality to impute missing values. We will impute five sets of data and combine the imputed results using the SAS MIANALYZE procedure to obtain a valid estimate of the confidence limit and treatment effect.⁸⁵ When data are missing for items within scale scores, we will use recommended imputation procedures rather than deleting patients list-wise from the analysis.

Mediators and Moderators of Intervention Effects. We will use multivariate modeling to identify the mechanisms through which the intervention achieves effects on outcomes and differential effects across subgroups.⁸⁶ Initial models will include only treatment group as the predictor. Subsequent nested models will introduce potential mediators (such as the number of completed therapist sessions), and we will evaluate changes in the relationship between experimental condition and outcomes before and after covariates are introduced. Analyses of effect moderation will focus on baseline pain severity and comorbid diagnoses using standard approaches to evaluate interactions between these covariates and patients' experimental condition.⁸⁶ Significant interactions will be interpreted by plotting regression lines for predicted outcomes of patients with high and low values of the moderator.

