D.10 Limitations of the Design

The AI engine will only make productive decisions about patients' therapy if valid and reliable information about patients' progress is available. In this respect, the AI-CBT program is identical to clinicians who must rely on patient reports to judge treatment response after a change in management. The AI engine will be programmed to treat dramatic changes in step counts that are likely to be inaccurate as missing data. Missing data on step counts and CBT skill practice will result in conservative choices in the AI-CBT group which in the extreme will leave patients with weekly one hour telephone CBT identical to that received by control patients. In contrast to other applications of reinforcement learning (e.g., purchases among Amazon.com users), the AI engine in this intervention will only be receiving data on a relatively small number of patients and time points. As such, the system will learn relatively slowly for a given patient, especially for patients enrolled in the initial phases of recruitment. We expect that this will lessen the system's ability to maximize cost-savings by offering less resource intensive but equally effective alternatives to extended telephone CBT sessions. As such, the differences in per-patient treatment cost across groups will be a lower bound of what could be expected if the service were implemented in VA with larger samples of patients over longer periods of time. Veterans with chronic pain who have significant comorbidity or are not able to walk will be excluded, limiting generalizability. Sensor technology is continuing to evolve rapidly, and the feedback from IVR+pedometers will likely under-estimate the ability of AI-CBT to personalize treatments using more passive and accurate activity measures yet-to-be-developed.

E. DISSEMINATION AND IMPLEMENTATION PLAN

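### The before/after mediation model adds completed therapist sessions, a count the AI-CBT algorithm sets from the patient's own progress, so it does not estimate mediation and its bias has no fixed direction

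*Combined protocol and SAP*

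**What the plan says.** The mediation method is the same in protocol section D.9 and in the Data Analyses Plan, both under Mediators and Moderators of Intervention Effects. The first step is "Initial models will include only treatment group as the predictor". Next, "Subsequent nested models will introduce potential mediators (such as the number of completed therapist sessions"). The result is read as follows: "we will evaluate changes in the relationship between experimental condition and outcomes before and after covariates are introduced". Session count is the only mediator named.

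Other sections describe how AI-CBT patients come to have more or fewer live sessions:

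- B.7: "patients who need more intensive follow-up will be moved automatically to more time-intensive, therapist-delivered CBT", while those who progress move to lighter options.
- D.1: on the basis of IVR feedback, "AI-CBT will make recommendations to carefully step-up the intensity of each patient's CBT follow-up".
- D.6, Daily IVR Reports: step counts are the reward, and functioning and skill practice are the state inputs to each decision.
- D.6, Role of the Expert Panel, as an example of a constraint: "if the patient's activity level decreases more than 20% two weeks in a row, recommend two hour-long CBT session".
- D.10: "Missing data on step counts and CBT skill practice will result in conservative choices in the AI-CBT group", at the extreme leaving the patient on weekly one-hour calls.

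Control patients are offered 10 one-hour therapist calls (D.5). The adjustment described is for baseline differences between arms and, in the mixed model, for baseline RMDQ and design factors such as site and age (D.9). Daily progress data come from the IVR system, which covers intervention patients only (D.7).

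**The concern.** The change in the group coefficient measures mediation only if nothing drives both session count and 12-week RMDQ. In AI-CBT the design builds in such a driver. Patients who report poor functioning or falling steps are the ones moved to live contact, and poor functioning during treatment plausibly predicts a worse RMDQ. Randomisation protects the arm comparison. It does not protect the path from sessions to outcome, on which this method depends.

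The control arm helps little. Its count is 10 by design and varies only through attendance, so the count is partly a label for arm and the session slope comes mostly from AI-CBT patients.

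The trial asks whether therapist time can be cut without loss of benefit. A mechanism result saying that contact does nothing, does harm, or does more good than it really does would bear directly on staffing.

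**Working it through.** **The plan's own figure.** The documents give no figure for the mediation analysis. The nearest is the sample size, which reproduces. Control n = (1.96 + 1.2816)² × 4.5² × (1 + 1/1.37) / 2² = 10.507 × 20.25 × 1.730 / 4 = 92.0, taken up to 93. AI-CBT n = 93 × 1.37 = 127.4, taken up to 128. The total is 221, with 90.1% power by the noncentral t.

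**Inputs.** From the documents: SD 4.5 and allocation 128:93. Assumed, because the documents are silent: a true effect of -0.3 RMDQ points per session, no direct effect of arm, 1.5 extra sessions per SD of poor progress in AI-CBT, mean sessions about 4.5 (AI-CBT) and 8.9 (control), and control attendance SD about 1. The progress-outcome correlation is varied; multiplied by 4.5 it gives RMDQ points per SD of progress.

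**Truth under these inputs.** Difference in mean sessions = 4.5 - 8.9 = -4.4. Total arm effect = -0.3 × -4.4 = 1.32, all of it mediated. Adding sessions to the model should therefore take the arm coefficient from 1.3 to 0.

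**What the planned model returns.** In least squares, arm coefficient after = total - (session coefficient × difference in mean sessions) = 1.32 + 4.4 × session coefficient. The session coefficients below are simulated.

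| Correlation | RMDQ points per SD | Session coefficient (truth -0.3) | Arm coefficient after (truth 0) |
|---|---|---|---|
| 0.1 | 0.45 | -0.14 | 1.32 - 0.62 = 0.70 |
| 0.2 | 0.90 | +0.01 | 1.32 + 0.04 = 1.36 |
| 0.3 | 1.35 | +0.18 | 1.32 + 0.79 = 2.11 |
| 0.56 | 2.5 | +0.6 | 1.32 + 2.64 = 3.96 (simulated 3.9) |

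The last row also depends on how much the count varies for reasons other than progress. With residual SDs of 1 to 1.5 and means of 4.5 to 5 against about 9, the session coefficient is +0.4 to +0.7 and the arm coefficient after adjustment is 2.6 to 4.2.

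**A weaker true effect.** With -0.2 per session the true mediated effect is about +0.88.

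| Correlation | Estimated mediated effect | Chance of the wrong sign at N = 221 |
|---|---|---|
| 0 | +0.87 | 13% (sampling error alone) |
| 0.1 | +0.31 | 34% |
| 0.2 | -0.28 | 64% |
| 0.3 | -0.85 | 87% |
| 0.5 | -2.07 | 99.6% |

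Adding the progress measure that drives assignment, observed in both arms, restores -0.20 per session at every correlation. The trial does not collect that measure daily in control. With -0.4 per session the mediated effect is still +0.03 at 0.3 and reverses to -1.09 at 0.5. With no true session effect, a spurious mediated effect of -0.58 to -2.94 appears for correlations of 0.1 to 0.5.

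**Engagement.** The mediator is completed sessions. When completion also depended on engagement, and engagement improved outcome, a version with weekly decisions (-0.2 per session) gave mediated effects of 0.48 to 2.65 against a truth of 0.84 to 0.87, with no sign reversal. With -0.3 per session, correlation 0.3, control attendance SD 2.5 and engagement worth 1 RMDQ point per SD, the session coefficient was -0.37 and the arm coefficient went from 1.1 to -0.3. Sessions then look too helpful.

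**A related inconsistency.** B.7 starts AI-CBT patients with a one-hour session; D.1 and D.6 start them with IVR. The two must be reconciled, since the session count depends on it.

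**The case against.** The strongest reply concerns direction. A reader might infer that the analysis would tend to show therapist contact doing harm. The documents do not support that. Completion reflects engagement as well as assignment: the plan allows for 20% drop-out and says many Veterans leave CBT early. Choices are partly probabilistic (B.7), early enrollees get more one-hour sessions (D.6), and missing reports raise intensity (D.10), so part of the variation in sessions is unrelated to progress. The +0.6 and 3.9 arise only at a correlation near 0.56; at 0.1 the session coefficient keeps its correct sign. All of this stands. It makes the direction unknown, but it leaves the confounding in place.

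A second reply is that this is a mechanism analysis with no stated hypothesis or decision rule, that sessions are given only as an example, and that a cited methods reference may say more. The first part stands and limits the consequences. But session count is the only example given, and the text itself states the before/after comparison with no adjustment for progress and no sensitivity analysis.

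A third reply is that the obvious alternatives are not clean either. That also stands. Continued Skill Use is self-rated at follow-up, so it has no time order relative to the outcome. Weights built from steps, skill practice and functioning alone would miss other drivers of assignment, and the documents do not say that action probabilities are logged.

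**Conclusion.** The point holds as a bias of unknown direction. As written, the before/after comparison on completed therapist sessions does not estimate mediation, because the trial's own design assigns AI-CBT sessions from on-treatment progress and nothing planned accounts for that.

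The table's range is illustrative. It rests on the assumed effect per session, the algorithm's responsiveness and the mean session counts, none of which the documents give. A reversed sign is possible and not certain.

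It would also be wrong to infer that the main result is in doubt. The non-inferiority test, its sample size and the Aim 2 and Aim 3 comparisons between arms do not use this model.

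**What to change.** Remove the number of completed therapist sessions from the before/after mediator models, in both D.9 and the Data Analyses Plan, and draw no mediation conclusion from it.

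If sessions are studied, do so within AI-CBT. Adjust or weight for what drives assignment: weekly steps, skill practice, functioning, missing reports and enrolment order, plus the algorithm's action probabilities if they are logged. Label the analysis exploratory and add a sensitivity analysis for unmeasured mediator-outcome confounding. Do not offer Continued Skill Use as an unconfounded replacement; if it is used, label it exploratory too.

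The cost is SAP wording and slightly more analysis work. The plan also loses its one named mediator.

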The AI Engine. Patients' IVR-reported step counts, skill practice, and pain-related functioning will be accessed by the AI engine daily to update the probabilities the system uses to determine which treatment to recommend the next week. We will use a state-of-the-art "contextual bandit" AI algorithm (LinUCB) designed to make careful choices while learning quickly from a patient's treatment response as well as the experience of other patients with similar characteristics (see Appendix A for technical details).⁶⁷⁻⁷⁰ With increased interactions, the system will learn to tailor decisions more effectively to maximize population-level improvements in functioning while minimizing clinician time. In this way, AI-CBT will function similar to the best clinicians, who learn from experience within and across patients. In the context of the trial, this means that patients enrolled early will likely receive less personalized CBT courses that are relatively similar to the standard CBT approach (i.e., a greater number of hour-long sessions), while patients enrolled later will receive services that are more personalized and include a greater frequency of 15 minute therapist sessions and IVR sessions. To maximize the efficiency of this "learning curve": (1) patients will be recruited over a longer period than would potentially be necessary, so that AI-CBT can gain as much experience as possible from patients recruited first and apply that knowledge to patients entering the program later; and (2) patients will be randomized with a greater "N" in the AI-CBT group in order to maximize the system's experience (see power calculation). As part of our evaluation, we will compare outcomes across randomization groups separately for early versus later enrollees, in order to test the hypothesis that AI-CBT will result in greater efficiency over time. These analyses also will allow us to project program benefits if AI-CBT were implemented in VA for thousands of Veterans and multiple years of experience.

CBT Treatment Fidelity will be assessed using the Yale Adherence and Competence Scale (YACS),⁷¹ a validated scale that assesses therapist adherence and competence in delivering manualized behavioral therapy. [name] will rate audiotapes of 30% of all CBT therapist sessions to assure that treatment is consistent with the manual and will provide corrective feedback to the therapists whenever drift occurs.

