Intensity of Service Use (Specific Aim 2). We will compare service utilization by category (e.g., CBT therapist time, PCP visits, and pharmacy use) between groups. We will conduct a budget impact analysis⁸⁴ and will include the cost of the intervention (personnel, supplies, CBT therapist training, and IVR fixed/variable costs) as well as costs for specific medical care services likely to be affected. Data from CBT therapists time records will be combined with wage data from the VA Financial Management System to produce estimates of intervention-specific personnel costs. Costs associated with the use of specific medical care services, such as medications, will be obtained from the Decision Support System (DSS) files. Cost analysis will be conducted in accordance with the guidance provided by Mauskopf et al.⁸⁴ including the use of sensitivity analysis and scenarios that allow for varying assumptions about intervention uptake, compliance or component costs. All resource use and cost comparisons will be adjusted for any

observed differences in baseline characteristics. Because costs of resource utilization are usually skewed, alternative modeling techniques (e.g., log-transformed costs, negative binomial regression) will be used.

Intervention Engagement and Satisfaction with Care (Specific Aim 3). As in our prior research,⁴⁹ we will conduct extensive analyses of the process of intervention delivery in both arms. We will monitor the proportion of telephone CBT sessions that are completed, and we will determine the patient and session characteristics associated with patients' reports of skill practice. Patients in the AI-CBT group will report their satisfaction with aspects of the intervention (e.g., whether it provided information useful for achieving behavioral targets), and we will assess the correlation between satisfaction ratings and measures of: intervention engagement, patients' baseline characteristics, and changes in pain-related functioning. Differential dropout across groups will be examined using Kaplan-Meier curves and survival models.

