an even larger difference in clinician time than the first 50%, while still demonstrating non-inferiority in pain-related outcomes. Differences in pain related functioning and in clinician treatment time across treatment groups will be tested in this subgroup analysis after stratifying the sample into early versus later recruits.

Mediators and Moderators of Intervention Effects. We will use multivariate modeling to identify the mechanisms through which the intervention achieves effects on outcomes and differential effects across subgroups.⁸⁶ Initial models will include only treatment group as the predictor. Subsequent nested models will introduce potential mediators (such as the number of completed therapist sessions), and we will evaluate changes in the relationship between experimental condition and outcomes before and after covariates are introduced. Analyses of effect moderation will focus on baseline pain severity and comorbid diagnoses using standard approaches to evaluate interactions between these covariates and patients' experimental condition.⁸⁶ Significant interactions will be interpreted by plotting regression lines for predicted outcomes of patients with high and low values of the moderator.

Evaluating the Reliability of Patients' IVR Reports. We will evaluate the integrity of IVR-reported step counts and functioning by examining associations between IVR reports and baseline characteristics that the literature suggests would be associated with patients' functioning (e.g., baseline SF-12 scores, comorbid medical diagnoses, and age). We also will examine serial correlations across IVR reports under the assumption that all correlations between scores and proximal scores should be positive and roughly of equal magnitude controlling for the time difference between reports.

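### The trial's cost saving is called a lower bound, but if AI-CBT starts on IVR and steps up, the direction of the slow-learning effect is not established

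*Combined protocol and SAP*

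**What the plan says.** **The bound.** Protocol D.10 says that with few patients and time points the engine learns slowly, which reduces its ability to save cost "by offering less resource intensive but equally effective alternatives to extended telephone CBT sessions". From this alone it concludes, without condition, that "the differences in per-patient treatment cost across groups will be a lower bound of what could be expected" from a larger and longer VA roll-out.

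**The hypothesis.** D.9 and the SAP, both under Preplanned Subgroup Analysis, expect that "the second 50% of patients randomized will show an even larger difference in clinician time than the first 50" per cent, with non-inferiority retained.

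**The premise.** D.6, The AI Engine, expects that "patients enrolled early will likely receive less personalized CBT courses that are relatively similar to the standard CBT approach", with more hour-long sessions. It adds that the early/late comparison will be used to "project program benefits if AI-CBT were implemented in VA for thousands of Veterans and multiple years of experience".

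**The starting mode.** The documents differ:

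- B.7: every patient starts with one hour and moves to cheaper modes on progress.
- B.9: the simulations assume a one-hour start.
- SAP, Specific Aims and Hypotheses: patients are stepped down.
- D.1: AI-CBT starts with IVR and steps up to 15 minutes or an hour if necessary.
- D.6, AI-CBT Action Recommendations: week 1 is IVR; all three modes are open afterwards.

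**Missing data.** D.10 says missing reports lead to conservative choices that "in the extreme will leave patients with weekly one hour telephone CBT identical to that received by control patients".

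**Budget impact.** D.9, Intensity of Service Use, plans sensitivity analysis and "scenarios that allow for varying assumptions about intervention uptake, compliance or component costs". The engine's stage of learning is not named.

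**The concern.** D.10's argument and the early/late hypothesis both need an engine with little information to keep patients on long sessions. Learning then removes therapist time, and a trial with slow learning understates the eventual saving.

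Under D.1's rule the logic reverses. A patient begins on the cheapest mode, so a slow engine is late in adding therapist time. Learning then moves non-responders up, and a slow-learning trial could show a larger saving than a trained engine would.

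Therapist time is central to Aim 2, and the early/late comparison feeds the projection to VA. If the bound pointed the wrong way, VA could plan too few therapist hours. The logged time would still be correct; the error would lie in the direction of the conclusion drawn from it.

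**Working it through.** **Inputs from the documents.** Control time is 10 x 60 = 600 minutes (D.5). The modes are 60 minutes, 15 minutes and IVR (D.6). Response is nested: a patient who responds to a cheaper mode also responds to a dearer one (B.9).

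**Assumptions.** IVR costs 0 therapist minutes. The shares needing IVR / 15 minutes / one hour (p1/p2/p3) are 50/30/20, equal thirds, or 20/30/50. A trained engine picks the right mode from week 2. No drop-out.

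**The plan's own figure.** The bound carries no number. The nearest is B.9's forecast of less than half of 600 minutes, that is, under 300. A trained engine with a one-hour start uses 60 + 9(15·p2 + 60·p3) = 208.5, 285 and 370.5 minutes for the three mixes. The first two agree with B.9. The third does not, so its results below deserve least weight.

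**One-way ladder.** The untrained engine spends k weeks at each mode before moving one step, k = 1, 2, 3. Untrained minus trained minutes:

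- One-hour start: IVR-type 60(k-1) + 15k = 15, 90, 165; 15-minute type 45(k-1) = 0, 45, 90; one-hour type 0.
- IVR start: IVR-type 0; 15-minute type -15(k-1) = 0, -15, -30; one-hour type -[60(k-1) + 45k] = -45, -150, -255.

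For the IVR start, trained time is 9(15·p2 + 60·p3) and the trained saving is 600 minus that. Weighted by mix, for k = 1, 2, 3:

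| Mix | One-hour start | IVR start | Trained saving, IVR start | Saving overstated, IVR start |
|---|---|---|---|---|
| 50/30/20 | +7.5, +58.5, +109.5 | -9, -34.5, -60 | 600 - 148.5 = 451.5 | 9/451.5 = 2% to 60/451.5 = 13% |
| Thirds | +5, +45, +85 | -15, -55, -95 | 600 - 225 = 375 | 15/375 = 4% to 95/375 = 25% |
| 20/30/50 | +3, +31.5, +60 | -22.5, -79.5, -136.5 | 600 - 310.5 = 289.5 | 22.5/289.5 = 8% to 136.5/289.5 = 47% |

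A positive difference supports the bound; a negative one contradicts it. Counting 5 minutes per IVR week (D.6 gives a 2-5 minute message) changes no sign.

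**Early versus late.** If k falls from 3 in the first half to 1 in the second, mean AI-CBT time changes by -102, -80 and -57 minutes (one-hour start) or +51, +80 and +114 (IVR start). Only the first direction matches the hypothesis.

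**A second mechanism.** Suppose patients stay at the starting mode for 1, 3, 5 or 10 weeks and then move directly to the right mode, with IVR at 3.5 therapist minutes. With equal thirds the saving is 304, 237, 169 and 0 minutes (one-hour start) or 361, 406, 452 and 565 (IVR start). The directions are again opposite.

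**IVR in week 1, but no ladder.**

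- The untrained engine uses the three modes equally from week 2: 9 x 25 = 225 minutes. Minus trained time: 225 - 148.5 = +76.5; 225 - 225 = 0; 225 - 310.5 = -85.5. The sign depends on the mix.
- It uses one hour from week 2: 9 x 60 = 540 minutes. Minus trained time: +391.5, +315 and +229.5. The bound holds for every mix.

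So IVR in week 1 does not fix the direction. What matters is what an under-trained engine does from week 2.

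**The case against.** Neither the bound nor the hypothesis names a starting session. The premise they need is stated in D.6, and D.6 is coherent by itself: one IVR introduction, all modes open afterwards, and an under-informed engine leaning to hour-long sessions. On that reading both statements hold. The missing-data default also suggests that the designers treat hour-long therapy as the safe choice. D.6's example of an Expert Panel constraint would add two hour-long sessions after a sustained decline, with no learning required. Only D.1's step-up sentence points clearly the other way. This stands as a plausible reading, but the supplied text does not establish it over D.1. The missing-data default depends on missing reports, not on the engine's stage of learning.

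A reader might infer from the IVR-start column that the trial will overstate the saving. The documents do not support that. The ladder never overshoots or steps down, so under an IVR start its only possible error is too little therapist time. The negative signs are built in. The planned engine is a contextual bandit with probabilistic choices, which can also give IVR responders hour-long sessions.

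Harm is limited too. The hypothesis is to be tested, no one-sided test is specified, and the projection rests on observed data. D.10 concerns treatment cost, which includes technology, whereas the figures above count therapist minutes only. These points reduce the weight of the matter. They do not justify an unconditional bound that D.10 derives from slow learning alone.

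**Conclusion.** The unconditional lower bound is not supported by the design text taken as a whole. It holds if an under-trained engine favours hour-long sessions, and could fail if the engine follows D.1 and steps up from IVR. The initial policy after week 1 is not in the supplied text, and Appendix A may give it. The direction is therefore not established; overstatement is possible, not shown.

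The minute and percentage figures are illustrations under assumed patient mixes, and the 2% to 47% range also assumes a one-way ladder. Its top end uses the mix that fits B.9 least well; the other two mixes give 2-13% and 4-25%.

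The RMDQ comparison, the sample size and the logged therapist time are unaffected. The point is worth correcting because the bound would be carried into VA planning and the correction is cheap.

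**What to change.** 1. In D.10, replace the lower-bound statement with one saying that the trial difference may under- or overstate a trained engine's saving, depending on the starting policy.
2. Make B.7, D.1, D.6 (both the week 1 text and The AI Engine) and the SAP's Specific Aims and Hypotheses consistent with the policy as programmed. Leave D.10's missing-data default unchanged. No change to the algorithm is asked for.
3. In D.9 and the SAP, test the early/late hypothesis with a treatment-by-half interaction on therapist time, reported with a two-sided 95% CI. Differences within each half do not test it directly. Also report the share of AI-CBT weeks in each mode by enrolment order.
4. Add a budget-impact scenario in which trained-engine therapist time is higher than the trial average, and label B.9's forecast as assuming a one-hour start.

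**Cost.** Text edits, one model term, one descriptive table and one scenario. No extra patients, calls or therapist time are needed, since the mode is already set weekly for every AI-CBT patient (D.6). Basing the roll-out projection on the second half alone is optional: with about 80 of 160 AI-CBT patients, its CI widens by about sqrt(160/80) = 1.4 times.
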